14.2. Sample Size Justification

This is a pilot study for assessing the investigational test articles. As such, the sample size was not determined based on any power analysis with regard to the primary endpoint. The collected data will be used to design future trials.

14.3. Analysis Populations

Safety Population:

All subjects who are administered any test article excluding subjects who drop out prior to administering any test article. At least one observation should be recorded.

Per-Protocol Population:

All subjects who have successfully completed all visits and did not substantially deviate from the protocol as determined by the trial cohort review committee prior to database hard lock (Per-Protocol Population). Justification of excluding subjects with protocol deviations in the per-protocol population set will be documented in a memo to file.

Intent-to-Treat (ITT) Population:

All randomized subjects regardless of actual treatment and subsequent withdrawal from study or deviation from protocol. At least one observation should be recorded.

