5. TEST ARTICLE ALLOCATION AND MASKING

5.1. Test Article Allocation

This is a non-randomized study. The study lens (RMY-100) will be fit bilaterally to the Test group subjects at the second visit of the study only.

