6. STUDY INTERVENTION

6.1. Identity of Test Articles

The following contact lenses will be used in this study:

	Table	1: Test	Articles
--	-------	---------	----------

	Test
Name	RMY-100
Manufacturer	JJVC
Lens Material	Etafilcon A
Nominal Base Curve @ 22°C	7.9 mm
Nominal Diameter @ 22°C	13.8 mm
Nominal Distance Powers (D)	-1.00 to -5.50 D
87 57	in 0.25D step
Nominal Cylinder Powers (D) and Axes	N/A
Nominal ADD Powers (D)	N/A
Water Content	58 - 61%
Oxygen Permeability (Dk), Boundary	28.0
corrected, Edge corrected	
Modality in Current Study	Daily wear
Replacement Frequency	Daily disposable
Packaging Form (vial, blister, etc.)	Blister Pack

Per the study design, each subject in the Test group will likely use at least one (up to 4) lens per eye for lens fitting (including up to 3 lens power modifications). Therefore, it is estimated that up to 8 lenses per subject for up to 25 subjects, which is approximately 200 lenses, will be used for the study. The study lens will be worn for up to 3 hours for each subject in the Test group.

There will be no test article fit to the subjects in the Control group.

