13. ADVERSE EVENTS

13.1. Definitions and Classifications

Adverse Event (AE) – An AE is "any untoward medical occurrence, unintended disease or injury, or untoward clinical signs (including abnormal laboratory findings) in subjects, users or other persons, whether or not related to the investigational medical device.

Note 1 to entry: This definition includes events related to the investigational medical device or the comparator.

Note 2 to entry: This definition includes events related to the procedures involved. *Note 3* to entry: For users or other persons, this definition is restricted to events related to investigational medical devices."²

An AE includes any condition (including a pre-existing condition) that:

- 1. Was not present prior to the study, but appeared or reappeared following initiation of the study
- 2. Was present prior to the study, but worsened during the study. This would include any condition resulting from concomitant illnesses, reactions to concomitant medications, or progression of disease states
- 3. Pregnancy must be documented as an adverse event and must be reported to the clinical monitor and to the Sponsor immediately upon learning of the event

Serious Adverse Event (SAE) – An SAE is any untoward medical occurrence that:

- Results in death
- Is life threatening
- Requires in-patient hospitalization or prolongation of existing hospitalization
- Results in persistent or significant disability/incapacity (eg, a sight threatening event, a significant persistent or permanent change, impairment, damage, or disruption to the subject's body)
- Is a congenital anomaly/birth defect, or
- Requires intervention to prevent permanent damage (the use of the test article resulting in a condition which requires medical or surgical intervention to preclude permanent impairment of the body structure or a body function). Important medical events that may not result in death, be life-threatening, or require hospitalization may be considered an SAE when, based upon appropriate medical judgment, they may

jeopardize the patient or subject and may require medical or surgical intervention to prevent one of the outcomes listed in the above definition.

Diagnoses and conditions that are considered Ocular Serious Adverse Events include, but not limited to:

- Microbial Keratitis (MK)
- Iritis (including cells in the anterior chamber)
- Permanent decrease in best spectacle corrected visual acuity equivalent to 2 acuity lines or greater

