13.3. Documentation and Follow-Up of Adverse Events

The recording and documenting of adverse events (ocular and non-ocular) begins when the subjects are exposed to the test article, study treatment or study procedure. Adverse events reported before the use of test article, start of study treatment, or study procedures will be recorded as medical history. However, if the condition deteriorates at any time during the study it will be recorded and reported as an AE. Untoward medical events reported after the subject's exit from the study will be recorded as adverse events at the discretion of the Investigator.

Upon finding an adverse event, the Principal Investigator will document the condition in the subject record and in the eCRFs. He/she will complete the Adverse Event /eCRF.

Complete descriptions of all adverse events must be available in the subject record. All Adverse Events including local and systemic reactions not meeting the criteria for "serious adverse events" shall be captured on the appropriate case report form or electronic data system. All adverse events occurring while the subject is enrolled in the study must be documented appropriately regardless of relationship.

It is the Investigator's responsibility to maintain documentation of each reported adverse event. All adverse events will be followed in accordance with applicable licensing requirements. Such documentation will include the following:

• Adverse event (diagnosis not symptom)

- Drawings or photographs (where appropriate) that detail the finding (eg, size, location, and depth, etc.)
- Date the clinical site was notified
- Date and time of onset
- Date and time of resolution
- Adverse event classification, severity, and relationship to test articles, as applicable
- Treatment regimen instituted, including concomitant medications prescribed, in accordance with applicable licensing requirements
- Any referral to another health care provider if needed
- Outcome, ocular damage (if any)
- Likely etiology
- Best corrected visual acuity at the discovery of the event and upon conclusion of the event

In addition, if an infiltrate(s) is present, he/she will complete the Corneal Infiltrate Assessment eCRF. Where necessary, a culture of the corneal lesion will be collected to determine if the infection is microbial in nature. If cultures are collected, the date of culture collection and laboratory utilized will be recorded.

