14. STATISTICAL METHODS

14.1. General Considerations

All data summaries and statistical analyses will be performed using the SAS software Version 9.4 (SAS Institute, Cary, NC). Throughout the analysis of data, the results for each subject/eye will be used when available for summarization and statistical analysis. Unscheduled visits will be summarized separately and will be excluded from the statistical analysis.

Summary tables (descriptive statistics and/or frequency tables) will be provided for all baseline variables, efficacy variables and safety variables as appropriate. Continuous variables will be summarized with descriptive statistics (n, mean, standard deviation [SD], median, minimum and maximum). Frequency count and percentage of subjects or eyes within each category will be provided for categorical data.

All statistical analysis will be conducted on the per-protocol population defined in Section 14.3.

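### The Safety Population (Section 14.3) leaves out all Controls and any Test subject who stops before lens insertion, and Section 14.1 does not say which set the safety summaries use

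*Combined protocol and SAP*

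**What the plan says.** **Who is in the safety set.** Section 14.3 defines the Safety Population as "All subjects who are administered any test article excluding subjects who drop out prior to administering any test article", with at least one recorded observation. Table 1 in Section 6.1 lists one test article, RMY-100, and the section adds: "There will be no test article fit to the subjects in the Control group". Section 5.1 states: "The study lens (RMY-100) will be fit bilaterally to the Test group subjects at the second visit of the study only".

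**Whose adverse events are recorded.** Section 13.3 says that recording "begins when the subjects are exposed to the test article, study treatment or study procedure", and then: "All adverse events occurring while the subject is enrolled in the study must be documented appropriately regardless of relationship". In Section 13.1, a note to the adverse-event definition reads: "This definition includes events related to the investigational medical device or the comparator". The next note extends the definition to study procedures.

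**Which set the tables use.** Section 14.1 promises summary tables for safety variables, then states: "All statistical analysis will be conducted on the per-protocol population defined in Section 14.3". The per-protocol set in Section 14.3 requires completion of all visits without substantial deviation. Section 14.7 lists slit-lamp findings among the summaries and names no population. No section assigns a table to the Safety Population.

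**The concern.** The rule for recording events and the rule for counting subjects start at different points. Recording starts at the first study procedure, in both arms. Membership of the safety set starts when a lens is placed, which happens in one arm only and at the second visit only. The protocol therefore collects adverse events from people whom its only safety-labelled set cannot contain.

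The other sets do not close the gap. The per-protocol set drops subjects who do not complete, which includes those withdrawn for an adverse event. The intent-to-treat set in Section 14.3 is defined on randomized subjects, and nobody in this study is randomized.

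At stake is the completeness and traceability of the safety tables in a study that enrols children from age 7. Depending on which set the programmer picks, different recorded events disappear from the tables, and the plan gives no basis for choosing.

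**Working it through.** The plan gives no numerical figure to reproduce here, and Section 14.2 states that there was no power calculation. The check is a cross-reading of the definitions, followed by simple proportions.

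**Step 1: when a subject can enter each set.** The Test sequence in Section 7.2 is:
- Visit 1 procedures.
- Visit 2, 1 to 10 days later. Adverse events are reviewed at Step 2.1, the slit lamp is at Step 2.4, continuance is decided at Step 2.5, and the lens goes in at Step 2.9.

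Controls have Visit 1 only.

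| Subject | Events recorded under 13.3 | Safety set | Per-protocol set |
|---|---|---|---|
| Test, fitted, completes | Yes | In | In, if no substantial deviation |
| Test, event before Step 2.9, then fitted | Yes | In, earlier event included | In, if completes without substantial deviation |
| Test, fitted, then withdrawn for an event | Yes | In | Out |
| Test, discontinued before Step 2.9 | Yes | Out | Out |
| Control, completes the single visit | Yes | Out | In, if no substantial deviation |
| Control, withdrawn during the visit | Yes | Out | Out |

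Read literally, the intent-to-treat set holds none of these subjects.

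**Step 2: is the fourth row a real path?** Yes. At Step 2.4 a Grade 3 or higher slit-lamp finding stops the visit. The subject may return once and may then be discontinued. The same step calls for significant findings to be documented and followed as adverse events, and Section 13.1 lists Grade 3 or higher corneal findings among the ocular significant adverse events. A Test subject who leaves at that point can have a significant adverse event and belong to no populated analysis set.

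**Step 3: does Section 13.3 treat events before the lens as medical history?** One sentence there could suggest it: "Adverse events reported before the use of test article, start of study treatment, or study procedures will be recorded as medical history". But the sentence before it makes exposure to a study procedure sufficient to start recording, and Step 2.1 asks for adverse events since Visit 1 before any lens is inserted. For Controls the question does not arise, because they undergo study procedures and never use a test article.

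**Step 4: size.** Inputs are the enrolment and completion targets in Section 4.3: Test about 25 enrolled and at least 20 completing; Control about 20 enrolled and at least 15 completing.
- Controls outside the safety set at planned enrolment: 20 / (25 + 20) = 20/45 = 44.4%.
- Largest possible safety set: 25/45 = 55.6%.
- Controls outside at the completion targets: 15 / (20 + 15) = 15/35 = 42.9%.
- Adding Test subjects who leave before insertion: the documents give no number. Assume 0 to 25 − 20 = 5. Then 20 to 25 of 45, or 44.4% to 55.6%, are outside.

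**The case against.** The strongest reply is that the definition removes nobody from any table, because no table is tied to the Safety Population. Section 14.1 promises summaries of safety variables without that restriction. It also mentions data summaries and statistical analyses separately, and its per-protocol sentence covers only the latter. Controls who complete their one visit could appear in per-protocol summaries, and slit-lamp findings could be shown by arm. This stands. A reader might infer that Control events can enter no safety summary, or that safety cannot be reported by arm. The documents do not support either inference. What they show is that the population is unstated and that each candidate set loses some recorded events.

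A reader might also infer that every event before lens insertion in the Test arm is excluded. That is not so. Section 14.3 selects subjects, not events, and sets no time window. A Test subject with an earlier event who is later fitted stays in the set with that event.

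It is fair, too, that a set based on lens exposure is the right denominator for lens-related risk, and that collection under Section 13.3 and notification under Section 13.4 do not depend on analysis sets. No event is lost to oversight.

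Finally, one might be tempted to measure the gap by comparing upper bounds for zero events on 25 and on 45 subjects. The pooled figure would mix subjects exposed to the lens with subjects never exposed, so the two would not bound the same rate. The plan sets no safety hypothesis or precision target either. Such bounds should not be quoted.

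**Conclusion.** The point holds as an inconsistency in tabulation. All Controls, about 20 of 45 planned subjects (44%), and any Test subject who discontinues before Step 2.9 are outside the Safety Population although their adverse events must be recorded. If the per-protocol set is used instead, completing Controls return but subjects withdrawn for an adverse event are lost. Test subjects discontinued before insertion, and Controls withdrawn during their visit, are in neither set.

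The 44% rests on the approximate enrolment targets. The upper end of 56% rests on the assumption that all five Test subjects in the gap between enrolment and completion targets leave before insertion. These are shares of subjects, not of events; the documents give no expected event rate.

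Severity is minor. Safety is not a primary or secondary endpoint in Section 2.2, the wavefront and off-axis comparisons are unaffected, and event collection and reporting work as written. It still merits a correction, because no stated set holds every subject whose events the protocol requires to be recorded.

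**What to change.** - **Section 14.3:** define the safety set as all consented subjects who undergo at least one study procedure, summarised by arm. Keep subjects who received a study lens as a named subset for lens-related events.
- **Section 14.1:** state that adverse-event and slit-lamp safety summaries use this set, and limit the per-protocol sentence to the other analyses.

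The cost is a few sentences and one additional set of tables. It needs no new data, visits or subjects, and the primary and secondary analyses do not change.

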5.2. Masking

This is a non-masked study.

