14.9. Procedure for Handling Missing Data and Drop-Outs

Missing or spurious values will not be imputed. The count of missing values will be included in the summary tables and listings.

Subject dropout is expected to be one of the main reasons of missing data in this clinical trial. Past clinical trials don't provide the evidence that subject dropout is systematic or not-atrandom. To evaluate the impact of missing data, sensitivity analysis will be conducted using multiple imputation methods if the proportion of subject dropout is greater than the 15%. The SAS/STAT procedures PROC MI and PROC MIANALYZE will be utilized with a parametric regression method used to make at least 5 imputations.

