15. DATA HANDLING AND RECORD KEEPING/ARCHIVING

15.1. Electronic Case Report Form/Data Collection

The data for this study will be captured on electronic case report forms (eCRFs) using an EDC system (Bioclinica). An authorized data originator will enter study data into the eCRFs using the EDC system. Data collected on equipment that is not captured in EDC will be formatted to the specification of the JJVC database manager and sent to JJVC for analysis.

External Date Sources for this study include: Exported WAM sphero-cylindrical refraction measurements in the format of Excel files, Medmont corneal topography data in the format of raw data files (e.g., (.axl, .tgl, .dst, .hgt) and COAS wavefront aberration data in the format of raw data files (e.g., .DVB, .F8 and .WFB).

The clinical data will be recorded on dedicated eCRFs specifically designed to match the study procedures for each visit. Once completed, the eCRFs will be reviewed for accuracy and completeness and signed by the Investigator.

The sponsor or sponsor's representatives will be authorized to gain access to the subject recordation for the purposes of monitoring and auditing the study.

Edit checks, electronic queries, and audit trails are built into the system to ensure accurate and complete data collection. Data will be transmitted from the clinical site to a secure central database as forms are completed or updated, ensuring information accuracy, security, and confidentiality. After the final database lock, the Investigator will be provided with Individual Patient Profiles (IPP) including the full audit trail on electronic media in PDF format for all of the study data. The IPP must be retained in the study files as a certified copy of the source data for the study.

The content and structure of the eCRFs are compliant with ISO14155:2011.²

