16.3. Data Quality Assurance

Sponsor.

Steps will be taken to ensure the accuracy and reliability of data, include the selection of qualified investigators and appropriate clinical sites and review of protocol procedures with the Principal Investigator. The Principal Investigator, in turn, must ensure that all Sub-Investigators and clinical site personnel are familiar with the protocol and all study-specific procedures and have appropriate knowledge of the study article.

Training on case report form completion will be provided to clinical site personnel before the start of the study. The Sponsor will review case report forms for accuracy and completeness remotely during the conduct of the study, during monitoring visits, and after transmission to data management. Any data discrepancies will be resolved with the Investigator or designee, as appropriate.

Quality Assurance representatives from JJVC may visit clinical sites to review data produced during the study and to access compliance with applicable regulations pertaining to the conduct of clinical trials. The clinical sites will provide direct access to study-related source data/documents and reports for the purpose of monitoring and auditing by JJVC and for inspection by local and regulatory authorities.

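### Outcome-blind exclusions are not specified: a committee's undefined standard decides membership of the only analysed set, and nothing keeps endpoint values from it

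*Combined protocol and SAP*

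**What the plan says.** Section 14.1 (General Considerations) is categorical: "All statistical analysis will be conducted on the per-protocol population defined in Section 14.3". Under Section 14.3 (Analysis Populations), membership requires completion of all visits and that the subject "did not substantially deviate from the protocol as determined by the trial cohort review committee prior to database hard lock". The same section adds: "Justification of excluding subjects with protocol deviations in the per-protocol population set will be documented in a memo to file". It does not list the deviations that count, and it does not describe the committee's membership or what the committee may look at.

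Section 5.2 states: "This is a non-masked study". Under Section 15.1, instrument data held outside the EDC system are "formatted to the specification of the JJVC database manager and sent to JJVC for analysis", and the external sources named there include "COAS wavefront aberration data in the format of raw data files", which carry the primary endpoint. Section 16.3 adds: "The Sponsor will review case report forms for accuracy and completeness remotely during the conduct of the study".

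Section 10 requires the investigator to notify the sponsor when a deviation is identified, within 24 hours if it is major, and requires all deviations to be tracked. Major is not defined there and is not tied to the wording of Section 14.3.

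**The concern.** In a masked trial, settling exclusions before hard lock protects the comparison because the people deciding cannot link a subject to an arm and a result. Here the arm is known to everyone. The plan does not say that wavefront, off-axis refraction or accommodation values are withheld until the list of exclusions is fixed.

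No other analysis would reveal the effect of the exclusions. The ITT set in Section 14.3 consists of randomized subjects, but Section 5.1 says the study is not randomized. The Safety set requires exposure to a test article, and Section 6.1 says Controls receive none. The multiple-imputation sensitivity analysis in Section 14.9 is triggered by dropout above 15%, not by committee exclusions.

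With arms this small, one or two judgement calls could shift the primary contrast of RMY-100 with orthokeratology, and the report would contain no result against which to see the shift.

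**Working it through.** The plan gives no SD, effect size, power or margin (Section 14.2 says the size was not based on a power analysis), so there is no figure of its own to reproduce. Everything below is in SD units and assumes a common SD in the two arms.

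**Inputs.** Minimum completers are 20 Test and 15 Control (Section 4.3). The decision rule is a 95% confidence interval at each distance that excludes 0 on either side (Section 14.5).

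**Precision.** For a plain two-sample comparison on 20 + 15 − 2 = 33 degrees of freedom, the half-width is 2.035 × √(1/20 + 1/15) = 2.035 × 0.3416 = 0.695 SD.

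**Shift from exclusions.** Removing k subjects, each 2 SD from the arm mean on the same side, moves the mean of n subjects by 2k/(n − k).

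| Controls removed | Shift in Control mean | Share of half-width |
|---|---|---|
| 1 of 15 | 2/14 = 0.143 SD | 0.143/0.695 = 21% |
| 2 of 15 | 4/13 = 0.308 SD | 0.308/0.695 = 44% |

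**How often such subjects exist.** Under normality the chance of lying beyond +2 SD is 0.02275. The chance that at least two of 15 do so on a given side is 1 − 0.97725^15 − 15 × 0.02275 × 0.97725^14 = 1 − 0.708 − 0.247 = 0.045. This is before asking whether either subject has an arguable deviation, so the two-subject row is close to a worst case.

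**Bound on error rates.** A simulation of 20,000 trials used two normal arms with SD 1, 20 versus 15 subjects and a two-sample t-test at one distance. That test simplifies the planned mixed model and omits covariates. With no true difference, the two-sided false-positive rate was:

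| Subjects excluded | Worst-case choice made on outcome | Choice made without outcomes |
|---|---|---|
| 0 | 5.1% | 5.1% |
| 1 (up to 1 in the worst case) | 13.2% | 5.1% |
| 2 (up to 2 in the worst case) | 25.5% | 5.2% |

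The worst case lets the most favourable extremes be dropped from either arm, whether or not those subjects deviated. The outcome-blind column dropped Test subjects without regard to their values. Selection can also hide a difference: with an assumed true difference of 1 SD, the share of trials that stay significant falls from 80.8% to 71.2% with up to one exclusion and 60.3% with up to two.

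**The case against.** The strongest reply is that exposure is inferred. Section 15.1 gives no transfer date, does not say that the committee receives the instrument files, and describes the wavefront data as raw files rather than spherical aberration values by subject. That stands. A reader might infer that the committee will decide with results in view, or that the lock demonstrably fails to hide outcomes. The documents do not support this; they are silent on access.

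The controls are also real. An exclusion for deviation needs a deviation, and Section 10 has deviations notified and tracked as they arise, so the candidates are not picked freely at the end. Controls attend one visit and have few chances to deviate. These facts narrow the discretion. They do not remove it, because classifying a tracked deviation as substantial remains a judgement that nobody is required to make blind.

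Two further readings are tempting and should be left aside:

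- **Individual readings.** Section 14.9 says "Missing or spurious values will not be imputed", which might suggest that single readings can be discarded at will. That sentence only bars imputation and gives nobody authority to discard. Acceptance criteria may sit in the wavefront and autorefractor work instructions listed in Appendix D, whose content is redacted.
- **Hiding the arm from the committee.** This is largely unworkable. Test subjects have two visits and a lens fitting, Controls have one visit and no fitting, so most deviations would reveal the arm.

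Finally, this is an exploratory pilot with an instrument-measured endpoint (Sections 2.1 and 14.2). That lowers the consequence. It does not protect the choice of which subjects count.

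**Conclusion.** The point holds as a gap in procedure. The only set used for inference is settled under an undefined standard, in an unmasked study, with no provision that the decision be made without endpoint values and no usable fuller set beside it. Selection on outcome is possible and not shown.

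The shifts of 21% and 44% of the interval half-width rest on a common SD, the minimum completer numbers and outlying Controls who also have a deviation. The simulated error rates are ceilings on what discretion could do, and should not be read as forecasts. Given the pilot status and the existing controls, this is an improvement to consider and does not make the analysis invalid.

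**What to change.** In Section 14.3, add that the committee classifies deviations from listings that omit all wavefront, off-axis refraction and accommodation values, and that it signs and dates the exclusion list before those values are merged with subject identifiers for analysis.

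In Section 14.5, add a second run of the primary model on all enrolled subjects with an endpoint measurement, meaning lens on eye for Test and bare eye for Control. Report it beside the per-protocol result so that the effect of the exclusions is visible.

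The cost is protocol wording, one redacted listing for about 45 subjects (25 + 20 enrolled) before lock, and one extra model run. Visits, sample size and the model itself do not change.
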